Day	≤21 days prior to Visit C1D 1	D1	D2 b	D3	D8	D1 5	D1	D2 b	D3 b	D1 c, e	-	30 days after last dose	60 days after last dose	-
Before BNT411 infusion (on infusion days) or on day of visit	E1	X, E3,U a	X, E3,U a	X, U a	X, E3	X	X, E3,U a	X, (E3),U	X	X, E3	X, E1	X, E1	X, E1	X, E1,U
Start of infusion		Ud												
End of infusion (+5 min)		X, E3			X, E3		X, E3			X,E3				
Start of infusion + 1 hour (±5 min)		X					(X)							
Start of infusion + 2.5 hours (±10 min)		X			X		X			X				
Start of infusion + 4 hours (±15 min)		X			X		X			X				
Start of infusion + 6 hours (±15 min)		X, E3 a,			X		X, E3ª			(X)				
Start of infusion + 8 hours (±15 min)		X					(X)							

Note: Time points for blood and urine sampling are to be followed as closely as possible but time deviations no longer than 2 hours will not be reported as protocol deviations as long as the exact times of sampling and dose are known.

E1 – Single ECG assessment.

E3 – Triplicate ECG assessments.

X – Blood sampling.

U – Urine sampling.

UNS - Unscheduled visit.

- (X) Blood sampling will only be performed in potential additional patients enrolled to expand the cohorts for RP2D confirmation.
- (E3) Triplicate ECG assessment will only be performed in potential additional patients enrolled to expand the cohorts for RP2D.

<sup>a Sampling time and sample volume have to be documented.

<sup>b Time window for the Day 2 sample in the dose escalation is 24 hours  $\pm$  1 hour and for Day 3 sample is 48 hours  $\pm$  2 hours after the start of infusion on Day 1.

<sup>c PK and ECG must be obtained in Cycle 3, Cycle 5, Cycle 7, and every 4 cycles thereafter (i.e., Cycles 3, 5, 7, 11, 15, etc.). d 6-hour urine collection after start of BNT411 infusion and total volume collected should be documented.

<sup>e After C3D1, PBMCs (for immune phenotyping and TCR profiling) will no longer be collected. Collection of PMBCs at treatment discontinuation and/or unscheduled visits is only required if the patient discontinues trial treatment prior to C3D1.

Table 1-4: PK (blood and urine) sampling and ECG assessment in Part 1B

Treatment Cycle	Screening			Cycle 1				Cycle 2	2	Cycle 3 - N	Treatment Discontinuation	Safety follow-up 1	Safety follow-up 2	UNS

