#### 8.6.3 Electrocardiograms

Triplicate (during trial treatment) or single (at other time points) 12-lead ECG will be obtained as outlined in the SoA (see Section 1.3, Table 1-3 and Table 1-4) using an ECG machine that

automatically calculates the pulse rate and measures PR, QRS, QT, and corrected QT (QTc) intervals. For the assessment the subjects will be in the supine position, lying still and quietly until the assessment has been done.

In general, increases in QT/QTc to >500 ms or of >60 ms over baseline are commonly used as thresholds for potentially discontinuing trial treatment; consultation with a cardiologist should be considered for any such increases to determine whether they are clinically significant.

At each time point at which triplicate ECGs are required, 3 individual ECG tracings should be obtained as closely as possible in succession, but no more than 2 minutes apart. The full set of triplicates should be completed in less than 5 minutes.

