8 STATISTICAL ANALYSES

8.1 General considerations

Unless otherwise specified, the details mentioned are for trial Parts 1A and 1B. The summaries will be presented as cohort and total within trial part (Part 1A and Part 1B). The presentation of data for Part 2 will be included in a SAP amendment.

No formal statistical comparisons between cohorts/trial parts will be performed.

Continuous variables will be summarized by cohort and total (as specified) using the following descriptive statistics: number of patients with non-missing data (n), mean, standard deviation (SD), median, minimum (min) and maximum (max).

Categorical variables will be summarized by cohort and total (as specified) presenting absolute and relative frequencies (n and %) of patients in each category and the number of patients with missing data (missing category will be presented if there is one or more missing value). Percentages will be calculated based on the number of patients with non-missing data (n) in the particular analysis set as the denominator. The text (N=xx) in the tables denotes the number of patients in the analysis set within each cohort. For event-driven occurrence data (e.g., adverse event, concomitant medication, etc.) the percentages will be based on the number of patients in the analysis set (N). For reported visit data (e.g., gender, [Eastern Cooperative Oncology Group] ECOG performance status, etc.) the percentages will be based on the number of patients with non-missing values (n).

All data collected during the trial will be listed, the trial day will be presented as appropriate. The data will be sorted by trial part (Part 1A, Part 1B) cohort, patient number cycle (if applicable) and date of assessment (if applicable).

All analyses will be conducted using SAS® version 9.4 or higher.

Baseline is defined as last available value prior to first dose of any trial treatment (i.e., for Part 1A BNT411 and for Part 1B BNT411 or atezolizumab or carboplatin or etoposide).

Generally, if there are multiple assessments available for a particular day, the assessment that is closest to the day (and time if collected) of the first dose of any trial treatment (i.e., BNT411 or atezolizumab or carboplatin or etoposide) will be used as the baseline value in the summary/analyses.

Multiple values at post-baseline visits: if there are multiple post-baseline assessments available within a visit/day, the earliest value and corresponding date/time will be considered.

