Change from baseline: Unless and otherwise specified, will be calculated as follows:

Change from baseline = post-baseline assessment value – baseline assessment value.

If either the baseline or post-baseline assessment value is missing, the change from baseline is set to missing as well.

For the derivations of PK and PD data, see Section [8.6.1](#) and [8.6.2](#).

Duration (Other than “Trial Treatment Duration” defined in Section [8.5.1](#)) will be calculated as follows:

- Duration = last observation date – first observation date + 1.

For conversion of days to months or years the following rules will be applied:

- 1 month = 30.4375 days
- 1 year = 365.25 days

Trial Day and Treatment Day will be calculated for each trial part (1A and 1B) as follows:

- Trial day:
 - If assessment date < treatment start date then trial day = assessment date – treatment start date
 - If assessment date >= treatment start date then trial day = assessment date – treatment start date + 1
- Treatment Day = treatment date – date of first dose of BNT411 +1

That is, trial day 1 indicates the date of treatment initiation.

For BNT411, it is Cycle 1 Day 1 of Part 1A and Cycle 1 Day 2 of Part 1B. For atezolizumab, carboplatin and etoposide it is Cycle 1 Day 1 of Part 1B.

All trial data will be presented as collected in the eCRF/visit assigned in external data. No windowing of data for the purposes of assigning to a visit will occur.

Unscheduled assessments will be listed only and not included in summaries/analysis.

Handling missing data:

For the purposes of assigning treatment-emergent flag for adverse events (AEs), partial or missing AE dates will be handled as follows (trial treatment date is the earliest date of BNT411 in Part 1A and earliest date of atezolizumab, BNT411, carboplatin and etoposide in Part 1B).

- If the day of the month is missing, the onset day will be set to the first day of the month unless it is the same month and year as trial treatment. In this case, in order to conservatively report the event as treatment-emergent, the onset date will be assumed to be the first date of trial treatment.

- If the onset day and month are both missing, the day and month will be assumed to be January 1, unless the event occurred in the same year as the trial treatment. In this case, the event onset will be coded to the day and month of treatment in order to conservatively report the event as treatment-emergent.

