8.5.3 Laboratory assessments

All laboratory assessments except for PK and biomarkers will be processed by local laboratories. Summaries of all laboratory data will be based on Safety set for each trial part (Parts 1A and 1B) and total within each trial part.

For the purposes of summarizing and presentation in tables and listings, all laboratory values will be summarized by cohort and presented in System International (SI) units. If a laboratory value is reported using a nonnumeric qualifier e.g., less than (<) a certain value, or greater than (>) a certain value, the given numeric value will be used in the summary statistics, ignoring the nonnumeric qualifier. The data as collected will be presented in the listings.

Clinical laboratory data to be summarized includes hematology, biochemistry, urinalysis, coagulation factors and endocrine tests. The safety laboratory parameters to be assessed are listed in Section 10.2 of the CTP. The scheduled time points for assessment are outlined in the SoAs (Section 10.4.1)

Continuous clinical laboratory variables at each protocol scheduled visit and its change from baseline to each post-baseline visit will be summarized using descriptive summary statistics for each parameter listed in CTP Table 10-1 by cohort. Categorical variables will be summarized using n and %.

Laboratory values that are below or above the reference ranges will be flagged.

Abnormal and clinically significant, abnormal and not clinically significant, and normal laboratory values will be summarized for each parameter by visit and cohort.

All laboratory data will be presented in the data listings. Abnormal clinical laboratory values will be flagged in the listing.

Serology and pregnancy results will be listed only.

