8.5.5 ECG

Triplicate (during trial treatment) or single (at other time points) 12-lead ECG will be collected as shown in CTP Table1-4 and Table 1-5.

The triplicate ECG values will be listed only. For the summary at each time-point, the first assessment will be considered.

ECG variables to be summarized include heart rate, QRS, QTc, QTcF. Absolute values collected at each time-point, and its change from baseline to each post-baseline time-point (for BNT411 infusion days the value collected pre-infusion will be used for this summary) will be summarized using descriptive summary statistics for each parameter by cohort, visit and trial part.

ECG variables collected on BNT411 infusion days and its change from baseline (pre-infusion value at that visit) to each post-baseline time-point will be summarized for each time-point using descriptive summary statistics for each parameter by cycle, cohort, and trial part.

In addition, the number of patients with abnormal QT, and QTcF (number of patients in the following categories ≤ 450 ms, $450\text{-}480$ ms, $480\text{-}500$ ms, >500 ms, and increase ≤ 30 ms, $>30\text{-}60$ ms and >60 ms over baseline) will be summarized by cohort and visit for each trial part.

Additionally, the results of ECG interpretation (normal, abnormal not clinically significant or abnormal clinically significant) will be summarized with number and percentage of patients by cohort and visit. For the triplicate assessments, only the first assessment will be considered for the summary.

A listing of ECG data will also be provided.

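### ECG summaries use only the first of three tracings, and objective values recorded off schedule reach listings but no table

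*SAP*

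**What the plan says.** **ECG.** Protocol 8.6.3 specifies that at triplicate time points "3 individual ECG tracings should be obtained as closely as possible in succession", and mentions "increases in QT/QTc to >500 ms or of >60 ms over baseline" as commonly used thresholds. Protocol Tables 1-3 and 1-4 schedule the triplicates; ECGs at screening, treatment discontinuation, safety follow-up and unscheduled visits are single. SAP 8.5.5 states: "The triplicate ECG values will be listed only. For the summary at each time-point, the first assessment will be considered". It repeats the rule for the interpretation table: "For the triplicate assessments, only the first assessment will be considered for the summary".

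**Baseline.** SAP 8.1: "Baseline is defined as last available value prior to first dose of any trial treatment". It adds that, generally, the assessment closest to first dosing is used when a day has several.

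**Off-schedule values.** SAP 8.1: "Unscheduled assessments will be listed only and not included in summaries/analysis". The same section rules out windowing, so a visit entered as unscheduled stays unscheduled. The objective safety tables are built by visit or time point. For laboratory data, for example, abnormal and "normal laboratory values will be summarized for each parameter by visit and cohort". SAP 8.5.4, 8.5.5, 8.5.7 and 8.5.8 do likewise for vital signs, ECG, ECOG and eye examinations. Worst-case summaries exist only for adverse events (SAP 8.5.2).

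**Late Part 1B visits.** Protocol Table 1-2, footnotes 1 and 27 (repeated in SAP Table 6), asks for a separate treatment discontinuation visit and a separate safety follow-up visit if the backbone drugs stop at least 21 days after BNT411. Both are to be entered in the eCRF as unscheduled.

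**The concern.** Two kinds of data already collected do not reach the tables. Two of every three tracings at a triplicate time point are left out of the ECG summaries, and the SAP gives no reason. Replicates are taken to reduce measurement noise, and using one of them forgoes that gain.

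An objective value obtained only off schedule can be seen only in a listing. This covers dose-delay visits, symptom-driven eye examinations and the late Part 1B visits. In Part 1B there is also a mismatch: adverse events are collected and counted as treatment-emergent up to 60 days after the last dose of any of the four drugs, while measurements from the late visits in that same period enter no summary because of their eCRF label.

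At stake are the precision of the QTcF change statistics and the completeness of the supportive safety tables.

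**Working it through.** The plan states no figure on this point, so there is none to reproduce.

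**Triplicates in Cycles 1–2.** Part 1A (Table 1-3): Cycle 1 Day 1 pre-dose, end of infusion and 6 h; Day 2; Day 8 pre-dose and end of infusion; Cycle 2 Day 1 pre-dose, end of infusion and 6 h. That makes 3 + 1 + 2 + 3 = 9 mandatory time points. Part 1B (Table 1-4) gives the same count, with Days 2 and 3 in place of Days 1 and 2. Per part, 9 × 3 = 27 tracings are scheduled; 9 are summarised and 18 only listed.

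**Which baseline applies.** In Part 1A the Cycle 1 Day 1 pre-dose triplicate can serve. In Part 1B trial treatment starts on Day 1 but the first triplicate is on Day 2, so the scheduled baseline ECG is the single screening tracing.

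**Precision.** Let s be the SD of one tracing around the patient's value at that time point, and b the SD between time points. The documents give neither; s = 4–10 ms and b = 5–10 ms are assumptions. Replicate errors are taken as independent.

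- First tracing at both times: SD of change = √(2s² + 2b²)
- Mean of three at both times: √(2s²/3 + 2b²)
- Single baseline, mean of three afterwards: √(s²(1 + 1/3) + 2b²)

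For s = 8, b = 7.5: √(128 + 112.5) = 15.51; √(42.67 + 112.5) = 12.46; √(85.33 + 112.5) = 14.07 ms.

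| s / b (ms) | First tracing | Both means | Reduction | Reduction, single baseline |
|---|---|---|---|---|
| 4 / 5 | 9.06 | 7.79 | 14.0% | 6.7% |
| 4 / 10 | 15.23 | 14.51 | 4.7% | 2.3% |
| 8 / 7.5 | 15.51 | 12.46 | 19.7% | 9.3% |
| 10 / 5 | 15.81 | 10.80 | 31.7% | 14.4% |
| 10 / 10 | 20.00 | 16.33 | 18.4% | 8.7% |

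**False category entries.** With no true change and both values triplicates, the normal tail beyond 30 ms per patient and time point falls from 2.65% to 0.80% at 8/7.5, and from 6.68% to 3.31% at 10/10. Beyond 60 ms the largest value, at 10/10, is 0.135% with the first tracing and 0.012% with the mean.

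**Off-schedule values.** No arithmetic applies, because the documents give no frequency. Reading the sections together: unscheduled values are excluded (SAP 8.1), the late Part 1B visits are labelled unscheduled (Protocol Table 1-2), and no table takes a worst or any-time value (SAP 8.5.3–8.5.5, 8.5.7, 8.5.8). Such a value therefore reaches a table only if it is recorded as an adverse event.

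**The case against.** The case for leaving the plan alone is substantial. The protocol says how to obtain the triplicates, not how to summarise them. The first-tracing rule is pre-specified and unbiased, and no document promises a worst-value table. All of this stands; what remains is a gain in precision from data already in hand.

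The off-schedule gap is also narrow. Protocol 10.3.3 makes a laboratory or vital-sign abnormality an adverse-event matter if it signals disease, causes symptoms, changes trial treatment or needs intervention. It also requires the maximum intensity of each adverse event, and SAP 8.5.2 tabulates worst grade. All data are listed, by-visit continuous tables show minima and maxima, and escalation cohorts are small. This too stands. The remainder is objective values not recorded as adverse events.

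A reader might infer more from the text in three ways:

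- *That Part 1B routinely loses its end-of-treatment data.* The separate visits are worded as something that should be done, and only when the backbone stops at least 21 days after BNT411. BNT411's own discontinuation and 30- and 60-day visits are scheduled and tabulated.
- *That the SAP contradicts itself on the ECG baseline.* The closest-value rule in SAP 8.1 is a general one and the first-tracing rule in 8.5.5 is specific to ECGs. The choice of tracing is ambiguous, not contradictory.
- *That false QTc alarms are common at the protocol's 60 ms threshold.* Under the assumed SDs they are rare with either rule.

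One objection limits the remedy. A maximum QTcF-increase table gathers false findings as ECGs accumulate. At 8/7.5 ms, I simulated Cycle 1–2 triplicates plus two Cycle 3 triplicates, three single end-of-treatment and follow-up ECGs, and up to two unscheduled singles. About 8.5–10% of Part 1A patients and 12.5–14% of Part 1B patients would show a false rise above 30 ms. A rate from Cycles 1–2 alone would understate this, and single tracings bring back the noise that averaging removes.

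**Conclusion.** The point holds as a minor improvement to supportive safety tables. The ECG summaries carry avoidable replicate noise: three times the replicate variance of the mean if errors are independent, less of a penalty if tracings taken within five minutes are correlated. Under the assumed SDs, averaging reduces the SD of QTcF change by about 5–32% with two triplicates and 2–14% against the single Part 1B screening ECG. The benefit lies in the change statistics and the 30 ms category.

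Objective off-schedule values not recorded as adverse events are visible only in listings; how often this happens cannot be estimated from the documents.

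It would be wrong to conclude that dose decisions or the primary safety results are at risk. DLT counts, the MTD and the adverse-event endpoints do not use these summaries.

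**What to change.** 1. In SAP 8.5.5, use the mean of each triplicate, including a triplicate baseline, for heart rate, QRS and QTc/QTcF summaries and categories. This also settles which tracing is baseline. Interpretation is categorical and has no mean; no change is asked for there.
2. In SAP 8.1, map the late Part 1B discontinuation and safety follow-up visits to named visits, so that their values enter the by-visit tables.
3. Add per-patient worst-post-baseline summaries that include unscheduled values, for laboratory data, vital signs, ECOG and eye findings. For laboratory data, the reference-range or clinical-significance categories already planned will serve; CTCAE grade is an option if grades are derived, which SAP 8.5.3 does not currently plan.
4. If a maximum QTcF-increase table is added, show triplicate means separately from single or unscheduled tracings. State in words that a maximum over many time points raises the chance of a false rise above 30 ms, and that this chance grows with the number of ECGs. Do not attach a fixed rate taken from Cycles 1–2.

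The cost is SAP wording, a visit mapping and a few extra tables, with no new data collection. The main drawback is the multiplicity of any maximum table.

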8.2 Patient disposition

Unless otherwise specified, all of the summaries will be presented by cohort and total within each trial part (Part 1A and Part 1B).

For the screened patients, the number and percentage of patients having failed screening will be presented along with a summary of the primary reason for screening failure. A summary of reason for violation of inclusion/exclusion criteria will also be presented. This summary is not by cohort.

The number and percentage of patients enrolled by site will be presented. The number and percentage of enrolled and treated patients will be presented by country and site including the number and percentage of IPDs (by cohort and total within each trial part).

The number and percentage of patients in each analysis set will be summarized by cohort and total within each trial part.

For each analysis set (e.g., Safety set, DLT evaluation set, PK Full set, PK Evaluable set and PD set) the number and percentage of patients being excluded from the analysis set will be presented by cohort and total along with a summary of the reasons for exclusion based on the Enrolled set.

For the Safety set the number and percentage of patients who are still on-treatment and percentage of treated patients who are off treatment will be summarized. Patients who are “off treatment” will be the patients who are discontinued from treatment. Also, for the Safety set the number and percentage of patients discontinued from each trial treatment (BNT411, atezolizumab, carboplatin, etoposide) will be presented along with a summary of the primary reason for treatment discontinuation as reported in the eCRF. All summaries will be by cohort within each trial part.

The number of patients that entered/not entered safety follow-up 1 and safety follow-up 2 (defined as had at least one data point collected in safety follow-up 1, safety follow-up 2, respectively) and the number of patients that had early discontinuation from the trial together with the primary reason for discontinuation will be summarized for the patients in the Safety set by cohort and total within each trial part.

In addition, total number of deaths will be summarized by cohort and total within each trial part for the Safety set.

A listing of patient disposition (including discontinuation from each trial treatment (BNT411, atezolizumab, carboplatin, etoposide) and discontinuation from trial) will be presented.

A listing of Enrolled set patients that are excluded from the Safety, DLT evaluation, PK and PD sets will be presented.

A listing of enrolled patients with protocol deviations will be provided.

8.3 Baseline characteristics

8.3.1 Demographics

Demographic data will be summarized by cohort for patients in the Safety set for each part of the trial (Part 1A and Part 1B).

Age (years), will be summarized as continuous data. Age category <65, ≥65 years), gender (male vs female), childbearing potential, race (White, Black or African American, Asian, American Indian or Alaska Native, Native Hawaiian or Other Pacific Islander, Not reportable, Unknown and other) and ethnicity (Hispanic or Latino, Not Hispanic or Latino and Not reportable) will be summarized as categorical data.

A listing of demography will be provided.

Baseline characteristics will be summarized by cohort for patients in the Safety set for each part of the trial (Part 1A and Part 1B).

Height (cm), weight (kg), Body Mass Index (BMI (kg/m²)), body surface area (BSA (m²)), and Glomerular Filtration Rate (GFR, mL/min/1.73 m²), will be summarized descriptively. BMI category (<18 kg/m², ≥18 kg/m², <25 kg/m², ≥25 kg/m², <30 kg/m², ≥30 kg/m²) and Smoking status (has never smoked, current smoker, ex-smoker) will be summarized with frequency counts and percentage by cohort.

A listing of baseline characteristics will be provided.

